$$\text{Incidence rate} = 100 * \frac{n \text{ subjects with } \geq 1 \text{ event of interest}}{\text{sum}[\min(\text{exposure time}, \text{time to event})]}$$

The sum of min(exposure time, time to event) will be computed by summing up the minimum of exposure time or time to event per subject across all subjects for each treatment and dose as treated (defined in Section 2.1).

For analyses using first treatment as treated (total dapagliflozin, total saxagliptin, placebo), exposure time and time to event are defined as:

Exposure time (years) per subject is computed as (last date of exposure for that subject - date of first dose in the study + 1)/365.25. Time to event (years) for subjects having the event is computed as (date of onset of event – date of first dose in the study +1)/365.25.

For analyses using dose at onset of AE to account for the change in treatment and dose at the 2nd and 3rd randomisations, exposure time and time to event are defined as:

Exposure time (years) per subject for each treatment and dose as treated is computed as (last date of exposure to treatment and dose for that subject - date of first exposure to treatment and dose + 1)/365.25. Time to event (years) for subjects having the event whilst on the current treatment and dose is computed as (date of onset of event – date of first exposure to treatment and dose +1)/365.25.

For incidence rate analyses for events prior to rescue, if no event occurred prior to rescue medication initiation then the date of rescue medication initiation is used instead of last date of exposure.

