4.6.3.1 Observed and change from withdrawal baseline in HbA1c and FPG

Descriptive summaries of observed and change from withdrawal baseline in HbA1c and, separately, FPG for withdrawal baseline and post-withdrawal baseline visits will be provided. This analysis will include all data regardless of rescue medication initiation or adherence. No imputation will be performed.

4.6.3.2 Percentage of subjects who achieve or maintain a HbA1c level < 7% at the end of the withdrawal period

The number and percentage of subjects who achieve or maintain a HbA1c level < 7% at the end of the withdrawal period will be provided. This analysis will include all data regardless of rescue medication initiation or adherence. No imputation will be performed.

4.6.3.3 Time to glycaemic rescue medication or discontinuation of study medication due to lack of efficacy

A time-to-event analysis (where event is first use of rescue medication or discontinuation of study medication due to lack of efficacy, whichever is earlier) during the 52-week treatment period will be analysed. Date of first dose will be date of first dose in the randomised withdrawal period. Kaplan-Meier estimates will be calculated, and 95% CIs will be presented. No Kaplan-Meier plot will be presented for this analysis.

Rules for censoring are described in Section 4.1.11.

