4.7.1.3 Serious adverse events

All SAEs (including hypoglycaemic and type 2 DKA events classified as SAEs) will be described in narratives, regardless of investigator assessment of causality. SAEs with an onset from Day 1 of the ST period up to and including 30 days after the last dose date in period (or up to and not including the start date of the LT period (if applicable), whichever comes first, for the ST period) will be considered as occurring during ST period. For subjects treated during the LT period, SAEs with an onset from Day 1 of the ST period up to and including 30 days after the last dose date will be considered as occurring during the combined ST+LT period. For the randomised withdrawal period, this listing will include all deaths on and after the date of withdrawal baseline until the date of Week 52 or date of last visit + 30 days (if earlier than Week 52). Number of events and incidence rates adjusted for exposure time, as described in [Section 3.4.1](#), will be reported.

The following descriptive summaries will be provided by SOC, PT and treatment group separately for the ST, ST+LT and randomised withdrawal periods:

- Any SAE
- Any SAE, up to Week 32 (ST+LT period only)
- Any SAE excluding AEs following rescue medication use (sensitivity analysis)
- Any SAE related to study drug (not related, related [including SAEs with missing relationship to study drug])
- Any SAE leading to leading to discontinuation of study medication

For the combined ST+LT period, SAEs will also be summarised by treatment group received at the time of SAE onset. For placebo subjects re-randomised to switch to dapagliflozin (or saxagliptin), SAEs will be analysed in the placebo group to the beginning of the randomised withdrawal period and in the dapagliflozin (or saxagliptin) group if the event onset occurs during the randomised withdrawal period. SAEs PTs will be presented as incidence rate adjusted for exposure, as described in Section 3.4.1.

In addition, all SAEs will also be summarised for the post-study visit at Week 104 for the Treated Subjects Data Set regardless of rescue medication initiation. For the randomised withdrawal period, subjects going through the third randomisation will be presented using the Randomised Withdrawal Subjects Data Set and will be summarised separately for the three treatment comparisons described in Section 4.1.5.

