8.15 Overview of primary and sensitivity safety analyses

Table 24 Overview of primary and sensitivity safety analyses

Subgroup includes race, ethnicity, sex, age group using the randomisation strata, region, baseline antidiabetic treatment, baseline HbA1c, baseline BMI.

Parameter	Assessment	Short term period	Short term + Long term period	Withdrawal period: 1) For subjects initially randomised the dapagliflozin (or saxagliptin) group: High-dose dapagliflozin (or saxagliptin) vs High-dose dapagliflozin (or saxagliptin) + Metformin 2) For subjects initially randomised to the placebo group: High-dose dapagliflozin (or saxagliptin) vs Placebo + Metformin 3) Based on third randomisation (regardless of prior treatments)	Post-study visit Week 104
AEs	Overall AEs	Descriptive statistics + incidence rates Regardless of rescue Treated Subjects Data Set	Descriptive statistics + incidence rates Regardless of rescue Treated Subjects Data Set	Descriptive statistics + incidence rates Regardless of rescue Randomised Withdrawal Subjects Data Set For treatment regimens 1, 2 and 3	
		Sensitivity Descriptive statistics + incidence rates Prior to rescue Treated Subjects Data Set	Sensitivity Descriptive statistics + incidence rates Prior to rescue Treated Subjects Data Set	Sensitivity Descriptive statistics + incidence rates Prior to rescue Randomised Withdrawal Subjects Data Set For treatment regimens 1, 2 and 3	
			Up to Week 32 Descriptive statistics + incidence rates Regardless of rescue		

Parameter	Assessment	Short term period	Short term + Long term period	Withdrawal period: 1) For subjects initially randomised the dapagliflozin (or saxagliptin) group: High-dose dapagliflozin (or saxagliptin) vs High-dose dapagliflozin (or saxagliptin) + Metformin 2) For subjects initially randomised to the placebo group: High-dose dapagliflozin (or saxagliptin) vs Placebo + Metformin 3) Based on third randomisation (regardless of prior treatments)	Post-study visit Week 104
			Treated Subjects Data Set		
			Excluding subjects randomised to withdrawal Weighted analysis Treated Subjects Data Set		
			Subgroup Descriptive statistics + incidence rates Regardless of rescue Treated Subjects Data Set		
			Subgroup - Sensitivity Descriptive statistics + incidence rates Prior to rescue Treated Subjects Data Set		

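### The SAP's exposure-adjusted incidence rates have no period-limited person-time, although Table 24 lists overall-AE rates for the short-term, up-to-Week-32 and randomised withdrawal periods

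*SAP*

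**What the plan says.** SAP Section 3.4.1 sums, over subjects, the smaller of exposure time and time to first event, and gives two ways to measure them.

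- **Rule 1**, for analyses by first treatment as treated (total dapagliflozin, total saxagliptin, placebo). The definition opens "Exposure time (years) per subject is computed as (last date of exposure for that subject"; the full expression is "last date of exposure for that subject - date of first dose in the study + 1" and time to event is "date of onset of event – date of first dose in the study +1", each divided by 365.25.
- **Rule 2**, for analyses by dose at onset, written "to account for the change in treatment and dose at the 2nd and 3rd randomisations". Exposure is "last date of exposure to treatment and dose for that subject - date of first exposure to treatment and dose + 1".

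The only truncation given is at rescue, for the prior-to-rescue analyses.

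The events are limited. Section 4.1.7 restricts period summaries to the Table 8 cut-offs by onset date, and starts the withdrawal period at its own baseline. Table 8 has no row for exposure.

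The sections differ on which periods have rates:

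- Table 24 (Section 8.15) lists incidence rates for overall AEs in ST, ST+LT and up to Week 32. Its withdrawal-period entry reads "Descriptive statistics + incidence rates Regardless of rescue Randomised Withdrawal Subjects Data Set".
- Section 4.7.1.1 names overall-AE rates for ST+LT only, and as optional.
- Section 4.7.1.3 sets SAE windows for ST, ST+LT and withdrawal, then states: "Number of events and incidence rates adjusted for exposure time", as described in Section 3.4.1, will be reported. That sentence names no period, and Table 24's SAE rows list descriptive statistics only.

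Elsewhere the SAP does limit time to a period. Section 3.5.4 defines treatment duration separately for ST, ST+LT and withdrawal. Section 4.3.1 ends exposure at the last dose of the period concerned. For the withdrawal-period rescue analysis, Section 4.6.3.3 resets the clock: "Date of first dose will be date of first dose in the randomised withdrawal period".

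**The concern.** A rate per 100 patient-years means what it says only if events and time at risk come from the same window. Here the events are cut to the period and the time is not. A child who completes 52 weeks without an event in the first 26 would add a full year to the short-term denominator.

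The withdrawal period raises a further question. Section 2.2.6 groups its analyses by the third randomisation, so Rule 1 does not cover them by its own terms, and Rule 2 is reserved for dose-at-onset analyses. No rule is left. A programmer who borrowed one of the two would count time from before the metformin decision, on a different treatment for some children.

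At stake are absolute AE rates in a paediatric safety report, and whether rates can be compared between periods. One of these periods bears on the safety objective concerning monotherapy after metformin withdrawal.

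**Working it through.** The documents state no incidence rate or person-time total, so there is no planned figure to reproduce. The check applies Section 3.4.1 as written and compares it with person-time limited to the period.

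**Inputs from the documents.** Target days in SAP Tables 9 to 11: Week 26 = 183, Week 32 = 225, Week 40 = 281, Week 52 = 365.

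**Assumptions.** Every subject is treated to Day 365; the hazard is constant within the period; the withdrawal period starts the day after its randomisation visit. The share of subjects with an event, p, is not in the documents and is varied from 2% to 60%.

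**Period lengths L.** ST: 183 days. Up to Week 32: 225. Withdrawal from Week 32: 365 − 226 + 1 = 140. Withdrawal from Week 40: 365 − 282 + 1 = 84.

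**Rare-event limit under Rule 1.** Nearly everyone is event-free and contributes 365 days, so the reported rate is L/365 of the period-limited rate:

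- ST: 183/365 = 0.50
- Up to Week 32: 225/365 = 0.62
- Withdrawal from Week 32: 140/365 = 0.38
- Withdrawal from Week 40: 84/365 = 0.23

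The last two lines show what would happen if Rule 1 were borrowed; the SAP does not assign it there.

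**Worked example, p = 10%, ST.** Daily hazard h = −ln(0.9)/183 = 0.000576. Mean time at risk in the period = p/h = 173.7 days, so the period-limited rate is 100 × 0.10/(173.7/365.25) = 21.0 per 100 patient-years. Subjects with an event contribute on average (173.7 − 0.9 × 183)/0.1, about 90 days. As written, the mean is 0.1 × 90 + 0.9 × 365 = 337.5 days, and the rate is 100 × 0.10/(337.5/365.25) = 10.8.

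In the withdrawal period, subjects with an event also add all the days before withdrawal (225 or 281).

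| Period | Period-limited rate, p = 10% | Rule 1 rate, p = 10% | Ratio, p from 2% to 60% |
|---|---|---|---|
| ST | 21.0 | 10.8 | 0.50 to 0.62 |
| Up to Week 32 | 17.1 | 10.8 | 0.62 to 0.73 |
| Withdrawal from Week 32 (if borrowed) | 27.5 | 10.2 | 0.38 to 0.29 |
| Withdrawal from Week 40 (if borrowed) | 45.8 | 10.1 | 0.23 to 0.16 |

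**Rule 2 borrowed for the withdrawal period.** Share of an event-free completer's counted time that lies inside the period:

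- On the high dose since about Day 100 and kept on it: 140/266 = 0.53 (Week 32) or 84/266 = 0.32 (Week 40).
- On the same low dose, or on placebo, since Day 1: 0.38 or 0.23.
- Drug or dose changed at the third randomisation: 1.0.

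Rule 2 is therefore correct only for children whose drug or dose changed at that point. Its error would differ between the arms being compared.

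**The case against.** The strongest reply is that the body text mostly confines rates to ST+LT, where Rule 1 is appropriate. Section 3.4.1 says rates may appear where specified. Section 4.7.1.1 names ST+LT for the overall summary, and the passages on common preferred terms, AEs of special interest and marked laboratory abnormalities do the same. On this view Table 24 is an overview that lists too much. Period-specific durations exist in Sections 3.5.4 and 4.3.1, and Section 4.1 refers to separate table specifications, which are not available here.

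Much of this stands. It shows a conflict between Table 24 and Section 4.7.1.1, and that the repair is short. It does not supply the missing rule. Section 4.7.1.1 also repeats the overall summary up to Week 32, and Section 3.4.1 does not refer to the period durations.

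A reader might go further and infer three things that the documents do not support.

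- **That the plan will show excess AEs on monotherapy where none exists.** Under Rule 2, with an assumed first-AE hazard of 0.8 per year everywhere, placebo switchers would show 80 per 100 patient-years against about 28 (Week 32) or 17 (Week 40) in placebo continuers: ratios of about 2.9 and 4.7. But the SAP assigns Rule 2 only to dose-at-onset analyses, which it specifies for ST+LT, and the hazard has no source in the documents.
- **That the clock starts in the wrong place in every period.** ST and up to Week 32 do begin at first dose; only the end is unbounded.
- **That SAE rates by period are firmly planned.** Section 4.7.1.3 is unclear on this and Table 24's SAE rows list no rates.

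**Conclusion.** The point holds in limited form. The ST and up-to-Week-32 overall-AE tables fall under Rule 1 by its own terms. If the rates in Table 24 are produced as written, they are too low for completers, by about one half and just over one third when events are rare. Ratios between arms are roughly preserved provided later exposure is similar across arms, but rates cannot be compared between periods.

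For the withdrawal period the person-time is undefined rather than wrongly defined. Either rule, if borrowed, would count time before withdrawal. Rule 1 would also credit placebo time to the monotherapy group for children who switched from placebo.

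The sizes assume treatment to Day 365 and a constant hazard within the period. A subject who stops treatment within ST or before Week 32 adds no excess time to that period, so early discontinuation reduces the error there.

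These are descriptive summaries: Section 4.7.1.1 plans no test of AE rates between groups. Counts and percentages by period, and all primary and secondary efficacy inference, are unaffected. Severity is moderate.

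**What to change.** 1. In Section 3.4.1, define person-time within the analysis period. Start at the first dose in that period: Day 1 for ST, ST+LT and up to Week 32, and the first withdrawal-period dose for withdrawal. End at the earliest of first event, end of exposure in the period and the period cut-off. Take the dates from Sections 3.5.4 and 4.3.1, adding the Week 32 cut-off from Table 8.
2. State that in the withdrawal period this applies to the third-randomisation groups.
3. Reconcile Sections 4.7.1.1 and 4.7.1.3 with Table 24 on which periods have AE and SAE rates.

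The cost is a few lines of SAP text and one programming change. No new data are needed.

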3.4.2 Deaths

Deaths in the study include all deaths recorded on the disposition page of the CRF (i.e., reason for discontinuation is death), the AE page (events with fatal outcome), or the SAE page (SAEs that result in death).

3.4.3 Other safety events

3.4.3.1 Diabetic ketoacidosis

A DKA event will not be reported on an AE CRF page unless the event fulfilled SAE criteria, in which case it should also be reported in the SAE form. Separate pages to capture details of DKA events are contained within the CRF. Details include signs and symptoms, contributing factors, whether local labs were performed, and whether the event is classified as an SAE. Adjudication findings (definite DKA, probable DKA, possible DKA, not DKA) will also be provided for DKA events sent to the Adjudication committee.

3.4.3.2 Hypoglycaemia

Hypoglycaemia event will not be reported on an AE CRF page unless the event fulfilled SAE criteria, in which case it should also be reported in the SAE form. Hypoglycaemic events that meet SAE criteria will be recorded as SAEs by the Investigator in the AE CRF pages. Separate pages to capture details of hypoglycaemia events are contained within the CRF. Details include symptoms, contributing factors, blood glucose measurements during the episode, date and time of last meal, third party intervention, any treatment(s) received, and whether the episode is classified as an SAE. Any self-monitored blood glucose (SMBG) measurements taken by the subjects on the days that they experience hypoglycaemia symptoms will be recorded in the CRF.

Hypoglycaemia episodes will be classified using ADA¹ and International Society of Paediatric and Adolescent Diabetes (ISPAD)² categories. Derivation details based on the information collected in the separate CRF pages for hypoglycaemia are provided in the Appendix (Section 8.9).

3.4.4 Safety Laboratory tests

Blood and urine samples will be obtained at specified time points for laboratory evaluations (see Appendix Section 8.1) and will be performed by central and local laboratories. The central laboratory for this study will perform the analysis of all scheduled laboratory tests and will provide reference ranges for these tests. The following selected laboratory parameters will be summarised:

Haematology:

- Haematocrit,

- Haemoglobin,
- Platelet count,
- White blood cell (WBC) count,

Blood chemistry:

- Bilirubin, total,
- Alanine aminotransferase (ALT),
- Alkaline phosphatase (ALP),
- Aspartate aminotransferase (AST),
- Urate,
- Estimated GFR (eGFR) using Schwartz equation (derived by the central laboratory):
$$\text{eGFR (mL/min/1.73m}^2\text{)} = 0.413 \times (\text{height [cm]})/\text{serum creatinine [mg/dl]},$$
- Creatinine, serum,
- Electrolytes - sodium, potassium, phosphate, chloride, magnesium and calcium,
- Protein, total,

Urine Analysis:

- Albumin,
- Albumin to creatinine ratio,
- Glucose: creatinine ratio,
- Spot urine for glucose.

Additionally, eGFR will also be described by age group using the randomisation strata: ≥ 10 and < 15 years; ≥ 15 and < 18 years.

Fasting serum lipid panel:

- Cholesterol, total,
- Triglycerides,
- High density lipoproteins (HDL) cholesterol,
- Calculated low density lipoproteins (LDL) cholesterol.

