b The lead-in period should start within 6 weeks after completion of the screening visit, and may start as early as 2 weeks after completion of the screening visit if all laboratory results have been received.

Table 5.1-2: Short-term Procedural Outline (CV181375 [D1680C00019])

| Procedure | Day 1 ^a | Wk 2 ^{a,b} | Wk 6 ^a | Wk 12 ^a | Wk 14 ^{a,c} | Wk 20 ^a | Wk 26/ETD (early discontinuation of IP)/Rescue ^{a,c} | Notes |
|---|-----------------------|------------------------|----------------------|-----------------------|-------------------------|-----------------------|--|--|
| Eligibility Assessments | | | | | | | | |
| Inclusion/Exclusion Criteria | X | | | | | | | |
| Review concomitant medications / procedures | X | X* | X | X | X | X | X | *Assessed by phone |
| Safety Assessments | | | | | | | | |
| Physical Examination | | | | | | | X | |
| Targeted Physical Examination | X | | X | X | | X | | |
| Tanner Staging (Investigator determined/Self-reported) | | | | | | | X | See Appendix 3 |
| Vital Signs | X | | X | X | X | X | X | |
| Height | X | | X | X | | X | X | |
| Body Weight | X | | X | X | | X | X | |
| ECG | | | | | | | X | |
| Assessment of signs and symptoms of hypoglycemia episodes | X | X* | X | X | X | X | X | *Assessed by Phone |
| Serious Adverse Event Assessment | X | X* | X | X | X | X | X | *Assessed by Phone |
| Adverse Events Assessment | X | X* | X | X | X | X | X | *Assessed by Phone |
| Laboratory Tests | | | | | | | | |
| Standard Safety Laboratory Panel (Blood/Urine) | X | | X | X | | X | X | See Appendix 1 |
| Fasting Lipid panel | X | | | | | | X | Total cholesterol, triglycerides, HDL, and LDL |

Table 5.1-2: Short-term Procedural Outline (CV181375 [D1680C00019])

| Procedure | Day 1 ^a | Wk 2 ^{a,b} | Wk 6 ^a | Wk 12 ^a | Wk 14 ^{a,c} | Wk 20 ^a | Wk 26/ETD (early discontinuation of IP)/Rescue ^{a,c} | Notes |
|---|-----------------------|------------------------|----------------------|-----------------------|-------------------------|-----------------------|--|---|
| Fasting Plasma Glucose (FPG) ^d | X | | X | Х | | х | X | On Day 1, the FPG sample will be collected pre-dose only. At the Wk 6, 12, 20 and 26 visits FPG samples will be collected pre-dose and approximately 2 hours post-dose (± 1 hour) All samples will be drawn in the fasting condition. |
| HbA1c | X | | X | X | | X | X | Results masked following IP administration on Day 1 until after study completion |

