6.8.1 Adverse Events of Interest

The following are possible safety concerns associated with DPP-4 inhibitors and/or SGLT-2 inhibitors, which should be considered adverse events of interest and must be captured when spontaneously reported: amputations/peripheral revascularizations, changes in growth; drug-induced liver injury/marked hepatic laboratory abnormalities (including liver function test abnormalities accompanied by jaundice or hyperbilirubinemia); hypersensitivity reactions (including anaphylaxis, angioedema, exfoliative skin conditions); severe cutaneous adverse reactions (including bullous pemphigoid); genital mycotic infections; necrotizing fasciitis of the perineum (Fournier's gangrene); urinary tract infections (including urosepsis/pyelonephritis);

opportunistic infections; decreased lymphocyte and/or thrombocyte counts; oral soft tissue conditions (e.g., stomatitis); pancreatitis; cardiac failure (including hospitalization for heart failure); acute kidney injury, renal impairment and/or renal failure; volume depletion; bone fractures; hyperlipidemia; hypoglycemic events; hyperglycemic events; ketoacidosis; malignancies (including bladder cancer); and arthralgia.

For the purposes of regulatory reporting, based on whether AEs in the above categories meet the criteria for serious or nonserious AEs, they will be collected and reported according to the appropriate guidelines, as described above in Sections 6.1.1 and 6.2.1, respectively.

To ensure that data on amputations are systematically collected, amputations and underlying conditions relevant to amputation will be recorded on a specific eCRF page. The AE leading to amputation should be recorded in the eCRF as AE/SAE. Events potentially placing the subject at risk for a lower limb amputation ("preceding events") should also be recorded in the eCRF as AE/SAE whether or not an amputation has taken place. These will be collected on a dedicated eCRF page.

After the initial AE report, the Investigator is required to proactively follow each subject at subsequent visits/contacts. All AEs of interest will be followed until resolution, stabilization, the event is otherwise explained, or the subject is lost to follow-up.

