 - Anti-hepatitis A virus IgM
 - Reflex testing: Low positive and positive results require confirmatory testing.
- C-peptide
 - ◆ Reflex testing will only be performed in otherwise eligible GAD and IA2 antibody-positive subjects

Specialized Liver Panel:

For subjects who are being monitored frequently as a result of confirmed AST and/or ALT > 3X ULN, additional central laboratory tests will be performed within 3 days of receipt of confirmatory results. These laboratory tests will study the possible causes of the increased ALT and/or AST and/or TB, and may include, but are not limited to, the following tests:

- Hepatitis A IgM
- Hepatitis BsAg
- Hepatitis B Core Ab IgM
- Hepatitis C virus RNA or RIBA
- Hepatitis C Ab
- Hepatitis E IgM
- Epstein-Barr virus (EBV) IgM Ab
- Lactate dehydrogenase (LDH)
- Gamma-glutamyl-transpeptidase (GGT)
- Carbohydrate deficient transferrin (CDT)
- Prothrombin time (PT/INR)
- Iron Panel iron, ferritin, total iron binding capacity (TIBC)

- Immunology panel including Antinuclear Antibody (ANA), Anti-Smooth Muscle Antibody (SMA) and Anti-Liver/Kidney Microsomal Antibody (Anti-LKM)
- Anti-tissue Transglutaminase Antibody

Liver Discontinuation Panel:

For subjects who are discontinued from the study as a result of sustained elevated liver safety abnormalities, additional central laboratory tests will be performed at the time of Early Termination (End-of-Treatment) visit. Similar to the Specialized Liver Panel, these laboratory tests will study the possible causes of the increased ALT and/or AST and/or TB, and may include, but are not limited to, the following tests:

- Cytomegalovirus (CMV) IgM Ab
- Herpes simplex virus (HSV) 1 and 2
- Ceruloplasmin
- Toxoplasmosis
- Alpha-1 antitrypsin

For specific details regarding the Specialized Liver Panel and the Liver Discontinuation Panel laboratory tests, refer to the Central Laboratory Manual for this study.

Standard Safety Laboratory Panels:

Table Appendix 1: Standard Safety Laboratory Panels

Hematology

- Hemoglobin (g/dL, g/L)
- Hematocrit (%, V/V)
- Red blood cell (RBC) (x10⁶/UL, x10¹²/L)

RBC count indices:

- Mean cell volume (MCV) (fL)
- Mean cell hemoglobin (MCH) (pg/cell)
- Mean cell hemoglobin concentration (MCHC) (gHb/dL, gHb/L)
- White blood cell count and differential
- Platelet count (x10⁹/L)

Serum Chemistry

• AST (IU/L)

Table Appendix 1: Standard Safety Laboratory Panels

- ALT (IU/L)
- Alkaline phosphatase (ALK-P) (IU/L)
- Total bilirubin (mg/dL, μmol/L)

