8.7 Clinical laboratory variables

8.7.1 Marked abnormality criteria for safety laboratory variables

Clinical laboratory variables will be summarised and listed using the units listed here. The criteria for marked abnormality for each variable are listed in the following table. Note that a post-baseline laboratory value will be considered a MA only if it satisfies the specified criteria as described in Section 4.7.3.4.

Table 18 Marked laboratory abnormalities

Conventional (US) Units:

Clinical Laboratory variables	Units	Marked Abnormality Criteria	
		Low	High
Hematology			
Haematocrit	%	< 20.0%	> 55.0%
Haematocrit	%		> 60.0%
Haemoglobin	g/dL	< 6 g/dL	> 18 g/dL
Haemoglobin	g/dL		> 20 g/dL
Blood Chemistry			
Protein, total	g/dL		> 10 g/dL
ALP	U/L		> 3X ULN
ALT	U/L		> 3X ULN
AST	U/L		> 3X ULN
ALT	U/L		> 5X ULN
AST	U/L		> 5X ULN
ALT	U/L		> 10X ULN
AST	U/L		> 10X ULN
ALT	U/L		> 20X ULN
AST	U/L		> 20X ULN
Bilirubin, total	mg/dL		> 1.5X ULN if PreTx ≤ ULN
Bilirubin, total	mg/dL		> 2X ULN if PreTx > ULN
Glucose, Plasma Unspecified	mg/dL	< 54 mg/dL	> 350 mg/dL
Na (Sodium)	mEq/L	< 130 mEq/L	> 150 mEq/L
Na (Sodium)	mEq/L	< 120 mEq/L	
K (Potassium)	mEq/L	≤ 2.5 mEq/L	≥ 6.0 mEq/L
Creatinine	mg/dL		≥ 1.5X PreTx CREAT
Creatinine	mg/dL		≥ 2.5 mg/dL
Calcium	mg/dL	< 7.5 mg/dL	≥ 1 mg/dL from ULN and ≥ 0.5 mg/dL from PreTx CA
Magnesium	mEq/L	< 1 mEq/L	> 4 mEq/L
PO4 (Phosphate)	mg/dL	Age 17-65: ≤ 1.8mg/dL	Age 17-65: ≥ 5.6 mg/dL
Urine			
UACR (Urinary Albumin to Creatinine Ratio)	mg/g		> 1800 mg/g

Standard International Units

Clinical Laboratory variables	Units	Marked Abnormality Criteria	
		Low	High
Hematology			
Haematocrit	ratio	< 0.20	> 0.55
Haematocrit	ratio		> 0.60
Haemoglobin	g/L	< 60 g/L	> 180 g/L
Haemoglobin	g/L		> 200 g/L
Blood Chemistry			
Protein, total	g/L		> 100 g/L
ALP	ukat/L		> 3X ULN
ALT	ukat/L		> 3X ULN
AST	ukat/L		> 3X ULN
ALT	ukat/L		> 5X ULN
AST	ukat/L		> 5X ULN
ALT	ukat/L		> 10X ULN
AST	ukat/L		> 10X ULN
ALT	ukat/L		> 20X ULN
AST	ukat/L		> 20X ULN
Bilirubin, total	µmol/L		> 1.5X ULN if PreTx ≤ ULN
Bilirubin, total	µmol/L		> 2X ULN if PreTx > ULN
Glucose, Plasma Unspecified	mmol/L	< 3 mmol/L	> 19.4 mmol/L
Na (Sodium)	mmol/L	< 130 mmol/L	> 150 mmol/L
Na (Sodium)	mmol/L	< 120 mmol/L	
K (Potassium)	mmol/L	≤ 2.5 mmol/L	≥ 6.0 mmol/L
Creatinine	µmol/L		≥ 1.5X PreTx CREAT
Creatinine	µmol/L		≥ 221 µmol/L
Calcium	mmol/L	< 1.88 mmol/L	≥ 0.25 mmol/L from ULN and ≥ 0.13 mmol/L from PreTx CA
Magnesium	mmol/L	< 0.5 mmol/L	> 2 mmol/L

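### Lymphocyte counts are collected and are a named event of interest, but the SAP plans no by-arm laboratory table for them; neither lymphocytes nor platelets have a marked-abnormality limit

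*SAP*

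**What the plan says.** **Named concern.** Protocol 6.8.1 includes "decreased lymphocyte and/or thrombocyte counts" among the possible safety concerns of these drug classes and says that such events "must be captured when spontaneously reported". SAP 3.4.1 carries the same category into its list of adverse events of special interest (AEOSIs).

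**Collected.** The haematology part of the standard safety panel in Protocol Appendix 1 contains "White blood cell count and differential" and a platelet count. Protocol Tables 5.1-2 and 5.1-3 schedule the panel at Day 1 and at Weeks 6, 12, 20, 26, 32, 40 and 52. It is also drawn at screening and at early-discontinuation and rescue visits.

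**Summarised.** SAP 3.4.4 introduces its list with "The following selected laboratory parameters will be summarised". The haematology entries are haematocrit, haemoglobin, platelets and "White blood cell (WBC) count"; no differential appears. SAP 4.7.3 and 4.7.3.1 refer back to that list for by-arm values and changes from baseline. SAP 4.7.3.1 adds low/normal/high shift tables based on the lowest and highest values in each period.

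**Marked abnormalities.** SAP 8.7.1 states: "The criteria for marked abnormality for each variable are listed in the following table". In both unit systems, the haematology rows of Table 18 are haematocrit and haemoglobin only.

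**Other routes.** SAP 4.7.3 lists haematology data by subject, with out-of-range flags. Protocol 6.3 sends certain laboratory abnormalities to the adverse-event or SAE forms. SAP 4.7.1.1 tabulates AEOSIs by preferred term and treatment group.

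**The concern.** The plan names a falling cell count as an event of interest and has the central laboratory measure it throughout treatment, yet it schedules no side-by-side table of the measurements. Whether a fall is visible by arm then depends on each investigator's decision to report it.

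That decision is made child by child. A drug effect that lowers lymphocytes moderately in most of an arm may look unremarkable in every individual. Group summaries of change from baseline, or counts of children whose lowest value falls below the reference range, exist to show such a pattern. Total white cells are a weak substitute, because a lymphocyte fall can be offset by other cell lines.

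The plan also treats some comparable concerns differently. Hepatic, renal and lipid events of interest have by-arm laboratory tables as well as adverse-event tables (SAP 4.7.3.2 and 4.7.3.3; creatinine and eGFR through 3.4.4; 4.7.3.5).

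**Working it through.** There is no planned figure to reproduce. The check is to follow each cell count from collection to output.

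| Step | Source | Lymphocytes | Platelets |
|---|---|---|---|
| Named event of interest | Protocol 6.8.1, SAP 3.4.1 | Yes | Yes |
| In the standard safety panel | Protocol Appendix 1 | Yes, through the differential | Yes |
| On the list to be summarised | SAP 3.4.4 | No | Yes |
| By-arm values and change from baseline | SAP 4.7.3, 4.7.3.1 | No | Yes |
| By-arm shift table on lowest value | SAP 4.7.3.1 | No | Yes |
| Marked-abnormality limit | SAP 8.7.1, Table 18 | No | No |
| By-subject listing with flags | SAP 4.7.3 | At most | Yes |
| Adverse-event route | Protocol 6.3, SAP 4.7.1.1 | If reported | If reported |

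One of the two named counts therefore has by-arm laboratory tables, and neither has a marked-abnormality limit.

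**Two readings used above.** The shift-table paragraph in SAP 4.7.3.1 does not itself cite 3.4.4. I take it to follow the 3.4.4 list, because that list defines which laboratory parameters are summarised. The listing entry for lymphocytes is marked as at most because SAP 4.7.3 refers to haematology data without naming the differential.

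**Volume of data.** Scheduled visits are Day 1 and Weeks 6, 12, 20, 26, 32, 40 and 52, which makes 8. With 243 planned subjects, 8 × 243 = 1,944 differentials. Of these, 7 × 243 = 1,701 are after baseline. Both are ceilings: they assume no missed visits or dropout, and they ignore the exclusion of site 4910 from the main outputs (SAP 4.10). They show how much is collected and say nothing about how likely an effect is.

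**What the adverse-event route catches.** Under Protocol 6.3 a laboratory result is recorded if it is clinically significant or meets the SAE definition, leads to interruption or discontinuation of study drug, or needs specific corrective therapy. A fall that meets none of these enters no adverse-event table, whatever the average change in the arm.

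**Whether the narrowing is recorded.** Protocol 8.4.3.1 promises values and changes from baseline for clinical laboratory parameters without limiting them to a subset. SAP Table 12, which lists departures from the protocol, does not mention the differential.

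**The case against.** The strongest reply is that the concern is framed as an adverse event and is analysed as one. Protocol 6.3 requires any clinically significant laboratory result to be recorded, not merely those volunteered. Protocol 5.9 blinds only HbA1c and urinary glucose, so nothing in the text hides haematology results from investigators. SAP 4.7.1.1 then tabulates AEOSIs by arm for the short-term, combined and withdrawal periods, with incidence rates for the combined period. This stands, and it narrows the gap to falls that investigators neither consider significant nor act on.

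It can also be said that total white cells are summarised by arm, that the SAP openly selects its parameters, that neither document promises a laboratory table for each event category, and that the output specifications are separate documents (SAP 4.1) not available here. The first point helps only partly, since a total can hide a fall in one component. The next two are fair: this is a gap in coverage, not a broken commitment to a lymphocyte table. As for the last, separate specifications might include lymphocytes, but the SAP as written does not call for them.

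Finally, laboratory outputs here are descriptive, so any comparison means side-by-side summaries, and no efficacy result depends on them. That is correct.

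**Conclusion.** The point holds for lymphocytes. They are measured at eight scheduled visits and named as an event of interest, but as written the SAP gives no by-arm change-from-baseline, shift or marked-abnormality table for them. For platelets, only the marked-abnormality count is missing.

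Two stronger conclusions are tempting and unsupported. A reader might infer from the missing Table 18 rows that platelet falls also go uncompared between arms. They do not: platelets are on the 3.4.4 list and get by-arm change tables and lowest-value shift tables. A reader might also infer that the named concern cannot be seen in any planned table. Reported falls in either count should appear in the AEOSI tables.

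The remaining gap is lymphocyte falls, including a moderate shift across an arm, that no investigator judges clinically significant or acts on. The documents give no basis for estimating how likely that is. The conclusion assumes that the 3.4.4 list governs the shift tables and that no unseen output specification adds lymphocytes. Efficacy conclusions are unaffected. The change is worth making because the data are already held and the cost is small.

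**What to change.** Add absolute lymphocyte count to the haematology list in SAP 3.4.4, so that the by-arm change-from-baseline and lowest-value shift tables of 4.7.3.1 cover it. The shift table uses the central laboratory's reference range, so no new threshold is needed. If the laboratory reports the differential as percentages, which the documents do not say, derive the absolute count from the total white-cell count and state this.

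Optionally, add low marked-abnormality criteria for lymphocytes and platelets to Table 18. With two analytes in two unit systems, that is 2 × 2 = 4 entries. The documents give no cut-offs, so the sponsor would have to set them before unblinding. These entries would also feed the period, Week 32, withdrawal, weighted and treatment-at-onset summaries in SAP 4.7.3.4.

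If lymphocytes are left out on purpose, record the omission and the reason in SAP Table 12.

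The cost is one list entry and a few more descriptive tables, plus the four optional limits and their outputs. No new data collection is needed.
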